#### **9.4.5 Other study parameters**

Baseline comparison of the treatment groups with regard to demographic variables (such as age, gender, number of co-morbidities, smoking, alcohol use, etc.) and time of TIS treatment. These parameters will be assessed by using the Student-t test for normally distributed variables, and the Mann-Whitney U test for not normally distributed variables.

#### **9.4.6 Interim analysis**

After inclusion and follow up of 50% of the randomized patients an interim analyses will be conducted. A poisson regression model is used for our power analysis; See chapter 9.1.

The interim analysis is used to calculate the predetermined effect size, and whether more patients should be included depending on this effect size. Depending on the frequency of exacerbations at baseline and the effect size, a power analyses will be done by using the poisson regression model.

## **10. ETHICAL CONSIDERATIONS**

### **10.1 Regulation statement**

This study will be conducted in compliance with Good Clinical Practice (GCP), including the International Conference on Harmonization (ICH) guidelines and the most recent version of the Declaration of Helsinki.

All amendments to the protocol and informed consent forms must be reviewed by the local Independent Ethics Committee for approval before being implemented. In the event of any deviation from the protocol, the investigator must document the nature of and rationale for the deviation. Informed consent must take place prior to any study specific procedure or test. Written signed and dated informed consent will be obtained from each subject (or his/her legally acceptable representative) in accordance with GCP and with local regulatory and legal requirements. The completed informed consent will be retained by the investigator as part of the study records.

### **10.2 Recruitment and consent**

Patients will be asked to participate in this study by their own physician or the investigator at the time of the hospital visit or are contacted by phone. All patients receive the patient information letter and informed consent form during this visit or this information will be provided by mail.

Within one week the patient will be contacted. Any questions will be answered. If the patient is willing to participate to the study, an appointment at the outpatient department will be made. During this visit informed consent will be signed by both the patient and sub-investigator.

### **10.3 Objection by minors or incapacitated subjects (if applicable)**

Not applicable.

### **10.4 Benefits and risks assessment, group relatedness**

Low risk study according to the risk-classification as designed by the Dutch Foundation of University Medical Centres. The full risk classification (in Dutch) can be found in Appendix 4.

### **10.5 Compensation for injury**

The sponsor/investigator has a liability insurance which is in accordance with article 7, subsection 9 of the WMO.

The sponsor (also) has an insurance which is in accordance with the legal requirements in the Netherlands (Article 7 WMO and the Measure regarding Compulsory Insurance for Clinical Research in Humans of 23th June 2003). This insurance provides cover for damage to research subjects through injury or death caused by the study.

- € 650.000, -- (i.e. zes hundred and fifty thousand Euro) for death or injury for each subject who participates in the Research;
- € 5.000.000, -- (i.e. five million Euro) for death or injury for all subjects who participate in the Research;

- € 7.500.000, -- (i.e. seven million five hundred thousand Euro) for the total damage incurred by the organisation for all damage disclosed by scientific research for the Sponsor as 'verrichter' in the meaning of said Act in each year of insurance coverage.

The insurance applies to the damage that becomes apparent during the study or within 4 years after the end of the study.

### **10.6 Incentives (if applicable)**

Not applicable.

## **11. ADMINISTRATIVE ASPECTS, MONITORING AND PUBLICATION**

### **11.1 Handling and storage of data and documents**

All data will be collected by the researcher on the electronic Case Report Form (e-CRF). The data will be entered into a database, where subjects will be assigned a study number. Their personal information will not be entered into the database. A separate subject identification list, the Investigator Site File, will be kept by the investigator at the study site in case the study data needs to be linked to individual subjects.

All study data will be kept for 15 years. Blood samples and sputum samples will be stored for 3 years.

### **11.2 Monitoring and Quality Assurance**

The conduct of the study and data entries will be monitored by an external monitor, [name]. He will select a sample of cases and check them for irregularities. If any are found, the monitor may choose to select a larger sample or review all available data. He will report the irregularities to the sponsor who is responsible for correcting any mistakes.

All adverse events will be analysed periodically by the statistician of the DSMB. If SAE's or SUSARs are more common in the experimental arm compared to the control arm he will inform the sponsor and other members of the DSMB which may then take actions as described in chapter 8.5. All serious adverse events will be reported to the accredited METC.

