#### **8.2.2 Serious adverse events (SAEs)**

A serious adverse event is any untoward medical occurrence or effect that at any dose: Results in death; is life threatening (at the time of the event); requires hospitalisation or prolongation of existing inpatients' hospitalisation; results in persistent or significant disability or incapacity; is a congenital anomaly or birth defect.

Any other important medical event that may not result in death, be life threatening, or require hospitalization, may be considered a serious adverse experience when, based upon appropriate medical judgement, the event may jeopardise the subject or may require an intervention to prevent one of the outcomes listed above.

SAE will be reported by the participating centres, preferably by mail, as soon as possible to the coordinating investigator.

The coordinating investigator will report the SAEs through the web portal *ToetsingOnline* to the accredited METC that approved the protocol, within 15 days after the coordinating investigator has first knowledge of the serious adverse events.

SAEs that result in death or are life threatening should be reported expedited. The expedited reporting will occur not later than 7 days after the responsible investigator has first knowledge of the adverse event. This is for a preliminary report with another 8 days for completion of the report.

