### 8.2.3 Suspected unexpected serious adverse reactions (SUSARs)

Adverse reactions are all untoward and unintended responses to an investigational product related to any dose administered.

Unexpected adverse reactions are SUSARs if the following three conditions are met:

the event must be serious (see chapter 9.2.2); there must be a certain degree of probability that the event is a harmful and an undesirable reaction to the medicinal product under investigation, regardless of the administered dose the adverse reaction must be unexpected, that is to say, the nature and severity of the adverse reaction are not in agreement with the product information as recorded in: Summary of Product Characteristics (SPC) for an authorised medicinal product or Investigator's Brochure for an unauthorised medicinal product.

The coordinating investigator will report expedited the following SUSARs through the web portal *ToetsingOnline* to the METC:

- SUSARs that have arisen in the clinical trial that was assessed by the METC;
- SUSARs that have arisen in other clinical trials of the same sponsor and with the same medicinal product, and that could have consequences for the safety of the subjects involved in the clinical trial that was assessed by the METC.

The remaining SUSARs are recorded in an overview list (line-listing) that will be submitted once every half year to the METC. This line-listing provides an overview of all SUSARs from the study medicine, accompanied by a brief report highlighting the main points of concern.

The expedited reporting of SUSARs through the web portal *ToetsingOnline* is sufficient as notification to the competent authority. All participating centres receive SUSARs once a month by mail.

The expedited reporting will occur not later than 15 days after the coordinating physician has first knowledge of the adverse reactions. For fatal or life threatening cases the term will be maximal 7 days for a preliminary report with another 8 days for completion of the report.

In summary, patients report potential adverse effect/ event (AE) of the study drug to their own respiratory physician as well in their diary chart. The respiratory physician reports this adverse effect/event to the coordinating investigator within one week and in SAE (e.g. hospital admission) as soon as possible. The coordinating investigator will inform the METC as described before.

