### **8.5 Safety Committee/ Independent expert**

The safety committee consist of one member, called the independent expert who is independent of the set-up and execution of the trial. This independent expert will receive the definite protocol and all revisions. The independent expert will convene every three to six months and review the results, i.e. results split by experimental and control arms. The independent expert has the power to recommend termination of the study based on the evaluation of these results. There are typically three reasons an independent expert might recommend termination of the study: safety concerns, outstanding benefit, and futility. The primary mandate of this independent expert is to protect patient safety. If adverse events of a particularly serious type are more common in the experimental arm compared to the control arm, then the independent expert would have to strongly consider termination of the study. This evaluation has to be made in consideration of risk/benefit. In many cases, the experimental arm could cause serious adverse events, but the resulting improvement in survival could outweigh these adverse events.

The independent expert should inform the findings or conclusions to the study investigators by mail or e-mail. If there is any dispute between the independent expert and study investigators, the independent expert should notify the METC Noord-Holland.

The independent expert is:

[name] longarts, Heiloo

Email: [contact]

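### Section 11.2 gives the by-arm SAE comparison to a DSMB that the plan does not set up, and has the sponsor told of any excess on TIS, however small

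*Combined protocol and SAP*

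**What the plan says.** Section 11.2 (Monitoring and Quality Assurance) states: "All adverse events will be analysed periodically by the statistician of the DSMB". It continues: "If SAE's or SUSARs are more common in the experimental arm compared to the control arm he will inform the sponsor and other members". Those fellow board members may then act under 8.5. It gives no margin, minimum count or review step before the sponsor is told, and sets the timing only as periodic.

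Section 8.5 describes a different body: "The safety committee consist of one member, called the independent expert who is independent of the set-up and execution of the trial". On frequency and content: "The independent expert will convene every three to six months and review the results, i.e. results split by experimental and control arms". On reporting: "The independent expert should inform the findings or conclusions to the study investigators by mail or e-mail". Apart from 11.2, DSMB appears only in the abbreviation list. No board members, board statistician or charter are described.

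Under 8.2.2 an event is serious if, among other criteria, it "requires hospitalisation or prolongation of existing inpatients' hospitalisation". Section 8.2.3 uses admission as its example of what to report quickly: "in SAE (e.g. hospital admission) as soon as possible". No text exempts or separates admissions for exacerbation. Exacerbations are the primary endpoint, and hospitalisation is a further study parameter (7.1.3).

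**The concern.** There are three linked problems.

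First, the two sections name different bodies. The comparison in 11.2 is given to a statistician whom the plan does not appoint, who is to notify colleagues whom the plan does not appoint. The sponsor is the one recipient who certainly exists.

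Second, any numerical excess obliges a message to the sponsor, and that message reveals the direction of the arm difference. Silence after a scheduled review is informative too. The trial is double blind (section 3). An exacerbation counts only if the treating physician agrees that antibiotic and/or prednisolone therapy was required, and the treating respiratory physician adjudicates the criteria (7.3). Section 8.5 likewise sets no limit on the arm-level content of what goes to the investigators.

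Third, admissions for exacerbation enter the SAE count. If TIS reduces them, a total SAE count is pulled down on TIS and could offset serious drug reactions there.

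**Working it through.** Section 11.2 states no threshold, error rate or expected SAE rate, so there is no plan figure to reproduce. The inputs from the protocol are:

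- 29 patients per arm, with 52 weeks of treatment plus 4 weeks of washout (section 3).
- A calendar span from summer 2016 to 31 January 2020, about 43 months (section 3).
- Reviews every 3 to 6 months (8.5), borrowed here because 11.2 gives no interval.
- A rate ratio of 0.5 for exacerbations (4.4 and 9.1).

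SAE rates are not given and are assumed over a range.

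**Single look, equal true rates.** Person-time per arm is 29 × 56/52 = 31.23 patient-years. With independent Poisson counts of mean m = rate × 31.23, P(TIS > placebo) = (1 − P(tie))/2, where P(tie) is the sum of squared Poisson probabilities.

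- At 0.1 per patient-year: m = 3.12, P(tie) = 0.163, so (1 − 0.163)/2 = 0.42.
- At 0.4 per patient-year: m = 12.49, P(tie) = 0.080, so (1 − 0.080)/2 = 0.46.

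**Repeated looks, equal true rates.** The number of looks is 43/6, about 7, or 43/3, about 14. A simulation of 20,000 trials used cumulative counts, even entry over 30 months (assumed), 56 weeks of follow-up and no drop-out. The probability of at least one look with more SAEs on TIS was:

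| SAEs per patient-year (assumed) | 7 looks | 14 looks |
|---|---|---|
| 0.05 | 0.53 | 0.55 |
| 0.1 | 0.63 | 0.66 |
| 0.2 | 0.70 | 0.73 |
| 0.5 | 0.76 | 0.80 |
| 1.0 | 0.78 | 0.84 |

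Adding the plan's 30% drop-out leaves the result at about 0.6 to 0.8 for rates of 0.1 to 0.4.

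**Dilution by exacerbation admissions.** Assume 29 patient-years per arm, background SAEs of 0.05 per year in both arms, drug-related SAEs of 0.10 per year on TIS, and placebo exacerbation admissions of h per year. Assume also that the ratio of 0.5 carries over to admissions. Expected totals are 29 × (0.5h + 0.15) on TIS and 29 × (h + 0.05) on placebo.

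| h | TIS mean | Placebo mean | P(TIS > placebo) |
|---|---|---|---|
| 0.05 | 5.08 | 2.90 | 0.72 |
| 0.10 | 5.80 | 4.35 | 0.62 |
| 0.20 | 7.25 | 7.25 | 0.45 |
| 0.30 | 8.70 | 10.15 | 0.33 |

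With exacerbation admissions left out, the means are 29 × 0.15 = 4.35 and 29 × 0.05 = 1.45 whatever h is, and the probability is 0.85. With no drug harm the same restricted count (1.45 in each arm, P(tie) = 0.248) fires with probability (1 − 0.248)/2 = 0.38. The restricted count therefore separates harm from no harm, although it too fires by chance.

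**The case against.** *A safety notification should be sensitive, and nothing stops when it fires.* This stands. Section 11.2 creates a duty to inform, after which action is optional, and 8.5 calls for a risk/benefit judgement. The lack of a margin would be defensible if the notice went only to the person charged with that judgement. It is harder to defend when the notice goes to the sponsor.

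*The intended body is obvious.* Partly. Section 11.2 points to 8.5, and 7.7 and 12.2 also name the independent expert, so the expert is a reasonable reading. The statistician's role remains unassigned.

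*There are other safety checks.* This stands. A reader might infer that 11.2 is the only comparative check. It is not: 8.5 has the expert review results by arm and strongly consider termination if events of a particularly serious type are more common on the experimental arm. Serious events also go individually to the METC (8.2.2), and the annual report orders serious reactions by organ system (8.3).

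*Pooling is not written.* Correct. Section 11.2 names SAEs and SUSARs separately and prescribes no single total. The dilution argument is inferred from the SAE definition and the absence of any split. It bears mainly on serious reactions already in the product information, since those cannot be SUSARs. A reader might infer that the plan would miss real harm. The documents do not support that: the size depends on rates that they do not give, and the type-specific review in 8.5 is a second route to detection.

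*The information passed on may be slight.* Partly. What 8.5 sends to investigators may be conclusions only, and nothing says that GPs are told. The complaint is that no limit is set, not that figures are certain to be released.

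**Conclusion.** The mismatch between 11.2 and 8.5 is plain on the text and needs correcting. The disclosure problem also holds. Under equal true rates the rule as written would inform the sponsor at a single look with probability about 0.42 to 0.46, and at least once in roughly 53 to 84% of trials. The first range assumes 0.1 to 0.4 SAEs per patient-year. The second assumes 0.05 to 1.0 per patient-year, 30-month even accrual and the review interval of 8.5.

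The dilution point is weaker. Its direction follows if TIS reduces admissions, but its size (0.72 down to 0.33, against 0.85 on the restricted count) rests wholly on assumed rates.

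Two stronger readings should be set aside. A reader might infer that chance imbalances would stop the trial, but the rule only informs. A reader might also infer that treatment codes are revealed, but what is disclosed is the direction of a group difference. The cost is to blinding and credibility, and it is avoidable.

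**What to change.** 1. In 11.2, replace the DSMB references with the independent expert of 8.5.
2. State who prepares the by-arm tables. The plan already mentions an independent statistician (7.7 and 9.4.1). That person can do it, provided he or she is outside trial conduct. Section 9.4.1 pairs the statistician with the investigator for the analysis, so this needs confirming. State also how that person obtains the allocation, because 8.2.3 reserves code-breaking to the coordinating physician.
3. Show SAEs twice by arm: in total, and excluding admissions for protocol-defined exacerbation.
4. Replace the duty to inform the sponsor with a rule that arm-level figures stay with the independent expert and the METC, and that the sponsor and investigators receive only a recommendation. Apply the same limit to the reporting sentence in 8.5. Keep the route in 7.7 by which the expert reports serious safety concerns to the METC, so that METC access is not confined to disputes.

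No numerical margin is then needed, because an excess prompts the expert's judgement and not a disclosure. The cost is a change of wording in two sections, one extra table split from data already collected, and the named statistician's time. The sponsor sees less during the trial.

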### **11.3 Amendments**

Amendments are changes made to the research after a favourable opinion by the accredited METC has been given. Non-substantial amendments will not be notified to the accredited METC and the competent authority, but will be recorded and filed by the sponsor. All amendments will be notified to the METC that gave a favourable opinion.

A 'substantial amendment' is defined as an amendment to the terms of the METC application, or to the protocol or any other supporting documentation, that is likely to affect to a significant degree:

- the safety or physical or mental integrity of the subjects of the trial;
- the scientific value of the trial;

- the conduct or management of the trial; or
- the quality or safety of any intervention used in the trial.

All substantial amendments will be notified to the METC and to the competent authority.

Non-substantial amendments will not be notified to the accredited METC and the competent authority, but will be recorded and filed by all other amendments and will be notified to the METC that gave a favourable opinion.

#### **11.4 Annual progress report**

The sponsor/investigator will submit a summary of the progress of the trial to the accredited METC once a year. Information will be provided on the date of inclusion of the first subject, numbers of subjects included and numbers of subjects that have completed the trial, serious adverse events/serious adverse reactions, other problems and amendments.

#### **11.5 End of study report**

The investigator will notify the accredited METC of the end of the study within a period of 8 weeks. The end of the study is defined as the last patient's last visit.

In case the study is ended prematurely, the investigator will notify the accredited METC within 15 days, including the reasons for the premature termination.

Within one year after the end of the study, the investigator/sponsor will submit a final study report with the results of the study, including any publications/abstracts of the study, to the accredited METC.

#### **11.6 Public disclosure and publication policy**

The results will be published within a year after completing the study. The study is completed after the follow up of a year of the last person. The main article will be published in an international respiratory journal with a high impact factor. Due tot the CCMO-guidelines the Sponsor acknowledges the importance of public disclosure/publication of information collected or generated by the Institution or Principal Investigator, under the condition that public disclosure/publication takes place under the provisions of article 8 of the Clinical Trial Agreement, called the onderzoekscontract BATTLE.

## 12. STRUCTURED RISK ANALYSIS

### 12.1 Potential issues of concern

#### a. Level of knowledge about mechanism of action

The vicious cycle hypothesis of bronchiectasis argues that bacterial colonization of the normally sterile respiratory tract provokes and perpetuates airway inflammation. According to this hypothesis, if bacteria are the primary drivers of airway inflammation, bacterial clearance through the use of short- or long-term antibiotic therapy would be expected to reduce airway inflammation, allow airway healing, and modify the long-term course of the disease. There is strong evidence from CF bronchiectasis to support this view, with data suggesting that bacterial colonization is associated with airway inflammation and that antibiotic treatment during stability and at exacerbation can reduce markers of inflammation. Extrapolation from CF to non-CF bronchiectasis is difficult because the pathophysiology is different and the failure of recombinant DNase treatment to provide benefit in non-CF bronchiectasis demonstrates that responses to treatment can be very different in CF compared with non-CF bronchiectasis. Another point of uncertainty is the different pharmacokinetics in CF patients particularly for aminoglycosides and b-lactam-antibiotics when compared with normal individuals. The higher body clearance due to increased renal and non renal elimination demands that higher antibiotic doses are administered more frequently. However, differences between CF-patients and non-CF individuals in this context do not seem to be as large as used to be thought and may have been exaggerated by the lack of properly matched controls for clinical studies.

However numerous studies in CF patients have shown that TIS has a positive effect on lung function, quality of life and in some on the number of exacerbations. There are limited studies evaluating the effect of bacterial clearance in non-CF bronchiectasis. From earlier studies we know that bacterial load (e.g. *P.aeruginosa*) can be reduced by TIS. Bacterial killing effects markers of airways and systemic inflammation in patients with bronchiectasis and therefore decreases clinical symptoms such as cough, dyspnoea and sputum production. The reduction of these symptoms has a positive effect on the health related quality of life.

